- a. Does your YNHH privilege delineation currently include the **specific procedure** that you will perform? Yes No
- b. Will you be using any new equipment or equipment that you have not used in the past for this procedure? Yes No
- c. Will a novel approach using existing equipment be applied? Yes No

If you answered "no" to question 4a, or "yes" to question 4b or c, please contact the YNHH Department of Physician Services ([name]) for prior approval before commencing with your research protocol.

IMPORTANT REMINDER ABOUT RESEARCH AT YNHH

Please note that if this protocol includes Yale-New Haven Hospital patients, including patients at the HRU, the Principal Investigator and any co-investigators who are physicians or mid-level practitioners (includes PAs, APRNs, psychologists and speech pathologists) who may have direct patient contact with patients on YNHH premises must have medical staff appointment and appropriate clinical privileges at YNHH. If you are uncertain whether the study personnel meet the criteria, please telephone the Physician Services Department at [contact]. **By submitting this protocol as a PI, you attest that you and any co-investigator who may have patient contact has a medical staff appointment and appropriate clinical privileges at YNHH.**

SECTION I: RESEARCH PLAN

1. **Statement of Purpose:** State the scientific aim(s) of the study, or the hypotheses to be tested.

We propose to examine, in 172 women newly diagnosed with Stage I-III breast cancer who are not practicing the dietary and lifestyle guidelines, and who will receive neoadjuvant or adjuvant chemotherapy as part of their treatment, the effect of a 1-year dietary and physical activity guidelines intervention vs. usual care on the breast cancer outcomes described below. Women will be enrolled either before beginning chemotherapy or following the first chemotherapy infusion but prior to the second chemotherapy infusion (Time 0). Follow up visits will occur post chemotherapy (Time 1), at one-year post-diagnosis (Time 2), at two years post-diagnosis (Time 3) and at five years post-diagnosis.

Primary Endpoints: Adherence to Breast Cancer Treatments

Aim 1a: Chemotherapy completion rates (dose amount, number of dose reductions and dose delays)

Aim 1b: Adherence to endocrine therapy in women taking tamoxifen or Aromatase Inhibitors (AIs) at 12- and 24-months after enrollment

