Secondary Endpoints: Changes in Biomarkers, Body Composition, Quality of life, pathological complete response (pCR).

Aim 2a: Neuronal calcium sensor 1 (NCS1), Insulin and C-reactive protein (CRP) levels

Aim 2b: Body composition (body weight, BMI, body fat, lean body mass and bone mineral density)

Aim 2c: Changes in Quality of Life (QOL) including cognition

Aim 3: Change in the fecal microbiome

Aim 4a: Determine the association between skin carotenoids pre- and post-chemotherapy and the side effects of chemotherapy (e.g. nausea, neuropathy) in the usual care group.

Aim 4b: Examine the difference in the pre- to post-chemotherapy change in skin carotenoid levels between women randomized to intervention vs. usual care.

Aim 5: Determine pCR, defined as no evidence of viable invasive tumor cells at the primary tumor site and axillary lymph nodes in the surgical specimen, in patients receiving neoadjuvant chemotherapy.

Aim 6: Determine the effect of the coronavirus pandemic on diet, physical activity, cancer care and mental health of LEANer participants.

Exploratory Endpoints:

- Examine the difference in the pre- to post-chemotherapy change in blood-based immune markers between women randomized to intervention vs. usual care.
- Examine changes in epigenetic age acceleration (based on epigenetic clocks using >800,000, methylation sites quantitatively across the genome) and p16, both as biomarkers of aging, from baseline to post-chemotherapy in usual care women
- Evaluate the effect of the lifestyle intervention vs. usual care on change in epigenetic age acceleration and p16 from baseline to one-year.
- Determine the effect of the intervention on longer term (5-year) physical activity, diet quality (healthy eating index) and quality of life.
- Determine breast cancer recurrence and second primary breast cancer.

2. **Background:** Describe the background information that led to the plan for this project. Provide references to support the expectation of obtaining useful scientific data.

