*Biomarkers: Fasting blood (> 12 hours) will be collected at baseline, at completion of chemotherapy and at the 1- and 2-year clinic visit. (Yale in-person visit only) Two 10-ml red-top tubes will be collected for serum, and two 10-ml lavender-top tubes will be collected for EDTA plasma. Technicians will centrifuge the EDTA samples at 2,000 rpm for 15 minutes at 4°C within 1 hour of collection. Plasma and buffy coat will be separated and, along with the serum, will be transferred into cryovials and labeled with freezer-proof labels with participant ID #s and date. All specimens will be stored temporarily at 4°C after aliquotting prior to delivery to our freezer (within 2 days), and then stored at -80

degrees C until analysis. Each woman's baseline and follow-up samples will be assayed in the same batch, and an equal number of intervention and control samples also will be included in each batch. Appropriate blinded quality control samples (low and high levels) will be used to monitor the reliability of each assay.

Insulin will be measured in serum using an enzyme-linked immunosorbent assay (ELISA) kit (DSL-10-1600, Diagnostic Systems Laboratories, Inc., Webster, TX). *CRP* will be measured with direct chemiluminescent immunoassay on the Immulite analyzer (Diagnostic Products Corporation (DPC, Los Angeles, CA). *NCSI* levels will be analyzed in [name] laboratory at the YSM. In addition, a panel of over 200 proteins potentially related to neuropathy will be analyzed at MD Anderson Cancer Center.

Immune markers

Olink: 92 inflammation, immuno-oncology, and metabolism proteins will be measured in blood plasma samples using Olink Biosciences's multiplex proximity extension assay (PEA). The 96 protein targets include cytokines, chemokines, markers that have been implicated in immunotherapy response (e.g., PD-L1, LAG3), and tumor or immune cell metabolism (e.g., ARG1, FBP1). Protein levels will be expressed as normalized protein expression and \log_2 transformed prior to statistical analysis. The protein levels in the intervention group will be compared with standard of care controls.

RNAseq: mRNA will be extracted from buffy coats using the RNeasy Plus Kit (Qiagen) according to the manufacturer's instructions. RNA sequencing will be performed at the Yale Center for Genome Analysis (YCGA). Gene expression differences between intervention and standard of care samples will be determined using "DESeq2" R package.

Genome Wide Methylation for EAA

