The MethylationEPIC BeadChip (Illumina; San Diego, CA) will allow us to interrogate >800,000, methylation sites quantitatively across the genome at the Yale Center for Genome Analysis. A sample of pooled female DNA is routinely included on each BeadChip as a control throughout the experiment and assessed for reproducibility using a Pearson R² coefficient. We will set to missing data points with detection p-values >.001 and will exclude any samples with probe detection call rates < 95% as well as those with an average intensity value of either <50% of the experiment-wide sample mean or < 2000 arbitrary units (AU). To limit confounding due to positional effects, samples for each person will be run in the same row.

P16 Human p16 ELISA Kit (LSBio) will be used according to manufacturer's instructions.

***Stool collection:** A stool collection kit, collection and mailing instructions will be provided to each participant to collect a stool sample in their home as baseline, post chemo and 1-year. Stool will be returned by pre-paid Fed Ex delivery to the Yale School of Public Health. Samples will be frozen and then sent for analysis to outside laboratories (Metabolon and [name] at UCSD). Women who are randomized after their first chemotherapy session (but prior to their second session) will not be asked to complete the stool collection at baseline or thereafter as their stool microbiota may have been affected by the chemotherapy so change in microbiota would be uninterpretable.

Analysis of Chemotherapy Completion Rate: Chemotherapy completion rate will be assessed (via medical records in EPIC) as the average relative dose-intensity (RDI) for the originally planned regimen

based on standard formulas. We will measure the number and percent of patients requiring dose-adjustments, who have dose-delays, the reason for the dose-adjustment/dose delays (e.g. neuropathy or vacation) and the percent dose reduction for each participant and by group, similar to Courneya and van Waart's papers.(8, 9) All relevant data will be extracted from EPIC (electronic medical records).

Analysis of Pathologic Complete Response: Pathology reports will be used to evaluate residual tumor after neoadjuvant chemotherapy. Pathologic complete response will be defined as no evidence of viable invasive tumor cells at the primary tumor site and axillary lymph nodes in the surgical specimen, regardless of the presence of non-invasive breast cancer or DCIS (Tis); i.e., yT0/TisN0.

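### Baseline may fall after the first chemotherapy infusion; the plan handles this for stool but not for carotenoids, immune markers, p16/epigenetic age or baseline symptom scores, which matters mainly for the usual-care-only analyses

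*Combined protocol and SAP*

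**What the plan says.** Section I.1 (Statement of Purpose) sets the entry window: "Women will be enrolled either before beginning chemotherapy or following the first chemotherapy infusion but prior to the second chemotherapy infusion (Time 0". The Experimental Design paragraph of Section I.3 places the baseline visit in the same window, before the second infusion.

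For one measure the plan acts on this. Under Stool collection in Section I.3(c): "Women who are randomized after their first chemotherapy session (but prior to their second session) will not be asked to complete the stool collection". The rule covers the later visits too, and the reason given is that "stool microbiota may have been affected by the chemotherapy so change in microbiota would be uninterpretable".

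The other baseline measures carry no such rule:

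- **Blood.** "Fasting blood (> 12 hours) will be collected at baseline, at completion of chemotherapy", and again at 1 and 2 years. The exploratory immune-marker endpoint is to "Examine the difference in the pre- to post-chemotherapy change in blood-based immune markers between women randomized to intervention vs. usual care".
- **Skin carotenoids.** Measured at baseline and post-chemotherapy, then yearly. Aim 4a, in usual care only, is to "Determine the association between skin carotenoids pre- and post-chemotherapy and the side effects of chemotherapy". Aim 4b compares the arms on pre- to post-chemotherapy change.
- **Epigenetic age and p16.** One exploratory endpoint is change "from baseline to post-chemotherapy in usual care women".
- **Symptoms.** PRO-CTCAE and the neuropathy questionnaire are completed at baseline and post-chemotherapy.

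Section I.12 models the secondary outcomes as change from baseline, with the baseline value as a covariate.

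**The concern.** Each of these measures has one value before the post-chemotherapy visit, so that value has to serve as the starting point. In a woman enrolled late it is taken after an infusion and may already contain part of the effect under study. The plan accepts that argument for stool and is silent on whether it carries over.

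The plan's own Background makes the question reasonable. It cites data suggesting that chemotherapy raises p16, research suggesting accelerated biological aging after cancer therapy, and a fall in serum antioxidants after cisplatin with no reported change in dietary intake. PRO-CTCAE is a side-effect instrument, so a score taken after an infusion can record toxicity.

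At stake is the meaning of the two usual-care-only analyses. A mean change computed from mixed baselines can be too small. In Aim 4a, a late baseline could lower carotenoids and raise symptoms in the same women. Part of any association might then reflect who had already been infused.

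**Working it through.** **1. Is the timing handled elsewhere?** Three places could do so:

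- Randomization (Section I.3(d)) stratifies on number of cycles, hormone receptor status and HER2, not on enrollment before or after infusion 1.
- The covariates and effect modifiers in Section I.12 do not include it.
- The sensitivity analyses in Section I.12 concern missing data only.

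**2. Which analyses are exposed?**

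- *Usual care only* (Aim 4a; baseline-to-post-chemotherapy p16/epigenetic age): two kinds of baseline are pooled and there is no comparison arm, so the mixture passes into the estimate.
- *Between arms* (Aim 4b, immune markers, Aim 2a biomarkers): randomization should balance timing on average. The expected cost is extra variance and a less clear estimand.
- *Relative dose intensity*: not a change from baseline, so this point does not touch it.

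**3. How large for a one-arm mean change?** The plan states no figure to reproduce. Let D be the true mean change, f the share of women with a baseline after infusion 1, and g the share of D already present at that baseline. A late woman shows (1 − g)D on average and the others show D, so

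observed mean change = D × (1 − f × g), and the proportional understatement is f × g.

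Inputs:

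- g: not given. The Usual Care Group paragraph of Section I.3 says that about one-third of patients receive 4 cycles, and about two-thirds receive 4 cycles followed by 12 weekly cycles, which makes 16 infusions. *Assuming* change proportional to infusions, g is 1/4 = 25% or 1/16 = 6.25%. The average is (1/3 × 0.25) + (2/3 × 0.0625) = 0.083 + 0.042 = 0.125.
- f: not given. *Assumed* 25% to 75%, and equal across regimens, as is D.

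Results:

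- f = 0.25: 0.25 × 0.125 = 0.031, about 3%.
- f = 0.75: 0.75 × 0.125 = 0.094, about 9%.

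The contamination is uneven: a late woman on the short regimen loses 25% of her change, one on the long regimen about 6%.

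Proportionality need not hold for acute markers such as CRP or immune proteins. With g set at 25% to 50% and f at 10% to 50%, all assumed, the understatement runs from 0.10 × 0.25 = 2.5% to 0.50 × 0.50 = 25%.

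**4. Aim 4a.** This aim is an association, not a mean change, so the formula does not apply. The documents fix neither the direction nor the size of any distortion.

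**The case against.** The strongest reply is that the plan makes the stool argument for microbiota alone and may have reason to treat other measures differently. The Background says that little is known about chemotherapy's effect on carotenoid status or about NCS1 changes with chemotherapy. Nothing in the text shows that one infusion materially shifts methylation age, p16 or skin carotenoids. This stands in part: extending the argument is an inference, and a reader should not conclude that the plan itself calls these other changes uninterpretable. But the plan gives no reason for the difference, and its Background points the other way for p16, biological aging and antioxidants.

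The wording also limits the point. A reader might infer that every baseline measure is presented as a pre-chemotherapy value. The aims use that language only for carotenoids and blood immune markers. For p16 and epigenetic age they say baseline, and Section I.1 openly defines baseline to include the later window. Aim 2a names marker levels, under a heading of changes.

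The late share may be modest. One Yale recruitment route hands out the brochure before chemotherapy starts. The clinic-schedule review sets no such limit, so the share remains unknown.

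Finally, in-person measures are optional, Yale-only and were suspended from mid-March 2020. Making a pre-infusion subset the primary analysis would shrink a reduced sample further and might select a different population. That is a fair argument against restriction as the main analysis, and the fix respects it.

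**Conclusion.** The gap is real and worth closing, but it is confined mainly to Aim 4a and one exploratory endpoint. As written, those usual-care-only analyses mix baselines from before and after infusion 1, which can understate mean change or distort the carotenoid-symptom association.

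The true size cannot be computed. The 3-9% for mean p16/epigenetic-age change rests on proportionality to infusions, the plan's approximate regimen mix and an assumed 25-75% late share; acute markers could differ.

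Two stronger readings are tempting and unsupported. The first is an understatement of more than a third: that requires, for example, 75% late and half of all change from one infusion (0.75 × 0.50 = 0.375), and the documents support neither input. The second is that the randomized comparisons are biased: timing should balance in expectation, so the expected harm there is noise.

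**What to change.** Add to Section I.12:

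1. Derive, for each baseline measure, an indicator of whether it was taken before or after infusion 1. Use the date of the measurement itself. Section IV lists the dates of all treatments among the data collected, and says that questionnaires and samples carry their date of collection.
2. For Aim 4a and the usual-care p16/epigenetic-age change, include the indicator in the model. Report the estimate in women with a pre-infusion baseline beside the all-women estimate.
3. Add the indicator as a covariate in the between-arm carotenoid, immune-marker and biomarker change models.
4. Report how many women fall on each side, so that the size of the problem can be seen. If the sponsor holds that the stool argument does not carry over to a given measure, say why.

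The cost is a few lines of analysis text and a smaller sample for the pre-infusion estimate. No new data are needed. For the genomic work the analysis text is the main lever left, since Section III.9 says this analysis was added after all relevant subjects were off study.

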1. "In the past month, how often did you take your medications as the doctor prescribed?" Possible responses are all of the time (100%), nearly all of the time (90%), most of the time (75%), about half the time (50%), or less than half the time (<50%). Nonadherence is defined as 75% of the time or less.
2. "In the past month, how often did you forget to take 1 or more of your prescribed medications?" Possible responses were never, once in the past month, 2 to 3 times in the past month, once per week, several times per week, and nearly every day. Nonadherence is defined as forgetting to take prescribed medications once per week or more.
3. "In the past month, how often did you decide to skip 1 or more of your prescribed medications?" Possible responses were the same as for question 2. Nonadherence is defined as deciding to skip medications once per week or more. The first will be the primary measure of non-adherence. (73,74) (75) If women switch AIs or from AI to tamoxifen, we will capture this, but classify them as having continued endocrine therapy and therefore adherent. All women who discontinue tamoxifen or AI will

be asked to indicate their rationale(s) via an interview-administered questionnaire. Note: The self-reported adherence questionnaire will be completed independent of whether a urine sample is collected.

Beliefs about Medication Questionnaire: Participants will complete the Beliefs about Medication questionnaire at baseline, 1 2 and 5 years. (78) We will also collect additional information about factors potentially influencing adherence at those 3 time points including: out-of-pocket costs, number and type of other prescriptions (from EPIC), degree to which the patient believes in the drug's efficacy, recurrence risk perception, and social support. These factors as well as age, education, smoking, comorbidities, chemotherapy, and any endocrine therapy side effects they experience during the trial will be examined in relation to endocrine therapy adherence.

COVID-19 Questionnaire

In July 2020, all women who are or who have been (if they agreed to future contact as indicated on the study consent form) participants in LEANer will be invited via email to complete an online or hard copy survey regarding the effect of the coronavirus epidemic on their cancer care, and their mental health, diet and physical activity. A link to the survey, which will be hosted on the Qualtrics platform, will be included in the email invitation with instructions on how to get the hard copy questionnaire if desired. The survey will take approximately 10-15 minutes to complete. A study staff member will follow up by email, text message or phone to confirm receipt of the invitation to complete the survey and answer any questions.

Newsletter: A newsletter will be mailed to all participants at 6-monthly intervals while enrolled in the study informing them of the progress of the study and providing relevant information with regard to breast cancer survivorship issues.

All assessments denoted * above are conducted at the in-person visits and are optional.

d) Randomization: Participants will be randomized into one of 2 study arms using a random permuted block design of varying block size in a 1:1 ratio (N=125 to intervention, 125 to usual care). To ensure participants with similar characteristics are equivalently assigned to the 2 groups, we will stratify on the following factors that may be associated with some of the study endpoints:

- i) chemotherapy regimen (≤ 4 cycles vs. >4 cycles)
- ii) hormone receptor status (ER/PR+ or not)
- iii) HER2 status (HER2+ve or not)

Resulting in six strata.:

- a) HR/PR+ve, HER2-ve, ≤ 4 cycles
- b) HR/PR+ve, HER2-ve, >4 cycles
- c) HR/PR-ve, HER2-ve, ≤ 4 cycles
- d) HR/PR-ve, HER2-ve, >4 cycles
- e) HR/PR+ve, HER2+ve, >4 cycles
- f) HR/PR-ve, HER2+ve, >4 cycles

The following study personnel will be masked to participant study arm: clinic medical staff performing the DXA scan and laboratory analysis.

Usual Care Group: Both our usual care group and intervention group will be provided with standardized breast cancer follow up care and materials regarding treatment (i.e., chemotherapy and endocrine therapy when relevant). Current chemotherapy regimens vary from 3 months to 5 months. About one-third of patients will receive four cycles of chemotherapy every 3 weeks, a total duration of ~3 months. About two-thirds of patients will receive four cycles of chemotherapy every 2 weeks followed by 12 weekly cycles of chemotherapy, a total duration of ~ 5 months. Each patient sees her medical oncologist at each chemotherapy session, and also at one- and two-months post-chemotherapy, and then every 3-6 months thereafter up to two years. Patients are seen semi-annually or annually; those on endocrine therapy are monitored by their oncologist semi-annually. Holiday cards will be mailed to all women while in study.

Lastly, we will also give women randomized to usual care a lifestyle intervention book and log book for breast cancer survivors and access to the associated online videos (approved for HIC protocol 1410014716).. Women will also be offered a counseling session with a registered study dietician at the end of the study.

Dietary and Physical Activity Guidelines Intervention Group:

When and Where: Patients receiving chemotherapy see their medical oncologist at least monthly during chemotherapy and then monthly or bi-monthly, ultimately tapering to semi-annually for several years. Thus, we have designed our intervention to be implemented in the breast clinic when the patient is seeing her medical oncologist. All intervention sessions can be completed by phone or video if this is the preference of the subject. Our LEAN study compared in-person lifestyle counseling to telephone-counseling, and found similar effectiveness on changes in diet and physical activity. For the proposed study, we have adapted our LEAN intervention to include a total of 16 x 30-min sessions over 12 months (3 times in the first month, then 2 times each month for months 2 through 5, and then 5 times over the next 6 months) timed with their oncology visit or via telephone or video (doxy.me) if preferred.

Content of LEAN Counseling Sessions: Our dietary intervention is to counsel women on eating the recommended diet for cancer prevention and control, which focuses on diet quality and nutrient density, which are essential, especially when and if appetite is changed or diminished from treatment. The intervention is based on the LEAN protocol, which was developed by Drs. [name], [name] and [name]. All counseling sessions will be conducted by a registered dietitian. The intervention represents a core curriculum, using motivational counseling to address behavior strategies such as self-monitoring, goal setting, stimulus control, problem solving, and relapse prevention training. The intervention sessions are based on constructs of social-cognitive theory. The nutrition counseling promotes a predominantly plant-based diet, with extensive education on skill building to track portion sizes, fat grams, reduce simple sugars (including sugar sweetened beverages), limit consumption of salty foods and increase dietary fiber intake, resulting in an increased nutrient-dense eating pattern (see Table 3). Maintenance of a healthy BMI is also one of the recommended DHHS, ACS and WCRF/AICR lifestyle guidelines and associated with lower breast cancer mortality. Thus, our LEAN intervention, focusing on portion control and primarily a plant-based diet, will likely lead to better weight management. All topics are accompanied by a homework assignment. Of these, recording daily food intake and physical activity are the most important. Reported portion sizes, grams of fat, added sugars and fiber from the food journal will be compared with individualized goals at each counseling session. Women will also receive our 16-chapter manual adapted from the LEAN manual and a set of adapted recipes. The five new sessions that will be offered

**Table 3. Lifestyle Guidelines
Physical Activity Guidelines**

1. 150+ min/week of moderate to vigorous intensity physical activity or 75 min/week of vigorous-intensity physical activity
2. Twice-weekly strength training
3. Reduce sedentary time

Dietary Guidelines

4. Eat a combination of 5+ fruits and/or vegetables servings/day
5. Reduce simple sugars
6. Limit consumption of processed and red meats to \leq 18 ounces/week
7. Limit alcohol consumption to 1drink/day or 8 drinks/week

will occur latter 6 months with 5 additional monthly sessions. These new topics will focus on issues relevant to women receiving therapy and the nutrition impact of treatment-related side effects. Topics to be discussed are: (1) Anticipating and managing treatment side effects: dysgeusia, nausea, mucositis, diarrhea, xerostomia change in appetite; body image changes, importance of hydration, managing liquid sugars; (2) Managing fatigue, meal timing, meal composition; (3) Managing expectations of others: Food is love, Comfort eating; (4) The importance of nutrition and strength training with endocrine therapy; and (5) Late effects of treatment: cardiac health, lymphedema, fatigue, fear of food, and fear of recurrence. Modifications to food texture, flavor and selection of tolerated nutrient-dense foods will be made on an individual basis to ensure adequate macronutrient and micronutrient food intake, and optimal glucose management.

Physical Activity: The physical activity program, similar to our LEAN and IMPACT studies, will rely on home-based exercise, with an emphasis on brisk walking and reaching a goal of 2.5 hour/week of moderate-intensity exercise and 10,000 steps walked each day. Reducing sedentary behaviors will also be encouraged through activities of daily living. The LEAN program increased physical activity levels by 116 min/week compared to 18 min/week among women randomized to usual care ($p < .01$). (24) For the trial, we have enhanced the physical activity program offered in LEAN, by including a home-based strength training program, developed by [name] for breast cancer survivors with lymphedema. (91). Each patient will be given a set of weights (3lbs and up) to use at home as instructed by the study health counselor. A series of study videos will be available online at the study website showing women how to complete each strength training exercise with and without weights, a LEAN Strength Training Program manual will also be provided. Participants will record the type and duration of exercise they do in their log book provided to them. We will also include a tool-box approach, as was done in the Diabetes Prevention Program, where we will provide participants with a 1-year membership to a YMCA close to their home to exercise in poor weather if they so wish, and Fitbits to motivate participants to increase their daily exercise. Participants will also be encouraged to complete the Livestrong program or a similar program at the YMCA

Goals of the Intervention: The goal of the intervention is for participants to adopt and practice the recommended dietary and physical activity guidelines. We will measure adherence to the dietary guidelines by whether participants meet the Healthy Eating Index 2010 (HEI-2010), as it aligns with the DHHS 2010 dietary guidelines, and has been found to be a valid and reliable measure of diet quality. We will update with HEI-2015 when available and we will also evaluate changes in intake of food group, total energy and energy from fat.

Procedures to Enhance Adoption of the Lifestyle Guidelines: Adherence will be assessed via attendance to counseling sessions, as well as by adherence to the diet and physical activity recommendations (assessed via questionnaire at baseline, 1, and 2 years). Women randomized to intervention will also complete a daily log book where they log their daily food, beverages and physical activity. At each counseling session, the dietitian will review the log book. Women randomized to intervention will also be given a Fitbit. The account will be accessible by both the subject and the research team to allow data to be accessed by the research team members. We have also developed an intervention book (adapted from the LEAN book). The books provided to the intervention group include information on skills to support behavior change. Consistent with social cognitive theory, (92) the information will emphasize increasing self-regulatory skills and using cognitive behavioral techniques such as cognitive restructuring, modeling, monitoring behavior, seeking social support, and self-reward. In summary, we designed the intervention based on our trials and to be scalable and implemented in the breast clinic.

To help those women in the intervention group comply with the intervention goals during and following the COVID-19 pandemic, all women who have been assigned to the intervention group will be emailed

- i) the link to the YouTube video in which [name] discusses the conduct of the LEANer study during the pandemic and how to adapt exercise regimens during COVID-19 restrictions. <https://www.youtube.com/watch?v=p7mA6tBlQz8>.
- ii) the link to video on safe grocery shopping practices during pandemic <https://youtu.be/3TtHg5XgZzI>

The videos will also be provided on the LEANer website tab accessible only by the intervention group participants.

Note: All patients will also be referred to the Yale Cancer Center Survivorship Clinic at the time of the post-chemotherapy visit, where they can if they wish attend up to 2 one-on-one sessions with our registered dietitian, [name], and physical therapist/exercise trainer, [name]. Holiday cards will be mailed to all women while in the study.

4. Genetic Testing

A. Describe

- i. the types of future research to be conducted using the materials, specifying if immortalization of cell lines, whole exome or genome sequencing, genome wide association studies, or animal studies are planned
 - Blood-based immune markers analyzed via Olink: 92 inflammation, immunoncology, and metabolism proteins will be measured in blood plasma samples using Olink Biosciences's multiplex proximity extension assay (PEA). The 96 protein targets include cytokines, chemokines, markers that have been implicated in immunotherapy response (e.g., PD-L1, LAG3), and tumor or immune cell metabolism (e.g., ARG1, FBP1). Analyses will be conducted at Yale.
RNAseq: mRNA will be extracted from buffy coats using the RNeasy Plus Kit (Qiagen) according to the manufacturer's instructions. RNA sequencing will be performed at the Yale Center for Genome Analysis (YCGA).
 - Epigenetic clocks using >800,000, methylation sites quantitatively across the genome) and p16, both as biomarkers of aging.
- ii. the plan for the collection of material or the conditions under which material will be received
Blood samples collected and stored as per study protocol (page 13 and 25) will be utilized for genetic analysis.
- iii. the types of information about the donor/individual contributors that will be entered into a database
Data collected as part of the study will be entered into the study databases. No additional data will be collected pertaining to genetic testing.
- iv. the methods to uphold confidentiality
The blood samples will be labeled with ID number and timepoint. Identifiable data will not be shared with the teams analyzing the blood samples. Data from the genetic analysis will be stored on password protected computers or on a shared drive with restricted access.

- B. What are the conditions or procedures for sharing of materials and/or distributing for future research projects?

Data exchanged between the researchers and internal organizations serving this project, such as the Yale Center for Genomic Analysis, will carry only the coded identifiers. Any sharing of materials and/or distribution for research projects will be required to have HIC approval and appropriate data sharing agreements will be put in place.

- C. Is widespread sharing of materials planned?

No, we do not plan widespread sharing of materials.

- D. When and under what conditions will materials be stripped of all identifiers?

Samples will be stripped of all identifiers if a participant withdraws from the study.

- E. Can donor-subjects withdraw their materials at any time, and/or withdraw the identifiers that connect them to their materials?

How will requests to withdraw materials be handled (e.g., material no longer identified: that is, anonymized) or material destroyed)?

Material will be destroyed if not yet anonymized if a participant wishes to withdraw their blood sample.

- F. Describe the provisions for protection of participant privacy

Samples will be identified only by ID. Identifiable data will not be shared with the teams analyzing the blood samples. Data from the genetic analysis will be stored on password protected computers or on a shared drive with restricted access.

- G. Describe the methods for the security of storage and sharing of materials

Material will be stored in a locked freezer at a Yale secure facility until analysis. Shared materials will be transported by study personnel or an approved courier. Samples will be identified only by ID and collection timepoint.

5. **Subject Population:** Provide a detailed description of the types of human subjects who will be recruited into this study.

We will enroll a total of 172 women who are planning to undergo chemotherapy at the Smilow Breast Center or a Smilow Care Center, Columbia University or Dana Farber Cancer Institute (DFCI) All women aged over 18 are eligible. Given treatments are often of a longer duration for stage IV breast cancer, women with stage IV will not be eligible. In addition, since a healthy diet and physical activity, independent of BMI, significantly contribute to breast cancer mortality risk reduction, we chose to limit inclusion criteria to women not practicing the diet and physical activity guidelines, but not to restrict on BMI. As material is only available in English, non English speaking women will not be included.

6. **Subject classification:** Check off all classifications of subjects that will be specifically recruited for enrollment in the research project. Will subjects who may require additional safeguards or other considerations be enrolled in the study? If so, identify the population of subjects requiring special safeguards and provide a justification for their involvement.

Children

Healthy

Fetal material, placenta, or dead fetus

- Non-English Speaking Prisoners Economically disadvantaged persons
 Decisionally Impaired Employees Pregnant women and/or fetuses
 Yale Students Females of childbearing potential

NOTE: Is this research proposal designed to enroll children who are wards of the state as potential subjects? **Yes** **No**

7. Inclusion/Exclusion Criteria: What are the criteria used to determine subject inclusion or exclusion?

Inclusion Criteria:

- Diagnosed with Stage I-III breast cancer
- Will receive neoadjuvant or adjuvant chemotherapy as part of breast cancer treatment
- Physically able to walk
- Able to complete forms, understand instructions and read intervention book in English
- Agrees to be randomly assigned to either intervention or usual care group
- Aged 18 or over

Exclusion Criteria:

- Women who have had their second chemotherapy infusion
- Women already practicing dietary or physical activity guidelines
- Are pregnant or intending to become pregnant in the next year
- Recent (past year) stroke/myocardial infarction or congestive heart failure
- Presence of dementia or major psychiatric disease
- Women who are malnourished (PG-SGA assessment)
- Participating in a meal replacement weight loss program
- Non English speaking

8. How will **eligibility be determined, and by whom?**

Study eligibility will be determined by study personnel in concert with Drs. [name] and [name].

9. Risks: Describe the reasonably foreseeable risks, including risks to subject privacy, discomforts, or inconveniences associated with subjects participating in the research.

Assessment of the risk associated with participating in the study can be categorized as minimal. The nutritionist/counselor will have weekly/monthly contact with each participant randomized to the dietary and physical activity guidelines intervention group for the first year of the study. During this time, the counselor will inquire about each participant's overall health and how she is adapting to the dietary and physical activity guidelines intervention program.

